- Exclude patients who had claims indicating TDD above 2000 units/day at any time in the pre-index or post-index periods.

Sample Selection Criteria for U-500R Device Switchers from Syringe to Kwikpen [Index Event 2]

- Include patients who had ≥ 1 claim for U-500R Kwikpen administration in the identification period (VHA and LCED: 01JAN2014-30JUN2017; Truven: 01APR2014-30SEP2017)–the first prescription claim for U-500R Kwikpen administration will be designated as the Index Event 2, and the date will be designated as the index date;
- Include patients who had ≥ 2 claim with an ICD-9/10-CM code (Appendix 1) for T2DM in any position (primary/secondary) at any time prior to the index date;
- Exclude patients who had both T1DM and T2DM, had no OADs (Appendix 1) other than metformin, and the ratio between the number of T1DM and T2DM claims > 0.5 at any time in the study period (VHA and LCED: 01APR2013-31MAR2018; Truven: 01JUL2013-30JUN2018);
- Include patients who were aged ≥ 18 years on the index date;
- Include patients who had continuous health plan enrollment with medical and pharmacy benefits for ≥ 9 months pre- and post-index event;
- Include patients who had ≥ 1 prescription claim for U-500R vial use in the 9-month baseline period;

[2018-7241 Study Identifier] Observational Study Protocol

- Include patients who had ≥ 1 HbA1c measurement within 90-day pre-index event or 30-day post-index event; and
- Include patients who had ≥ 1 HbA1c measurement after the 30-day post-index period;
 - Patients with ≥ 1 HbA1c measurement after the 30-day post-index and within 30 days prior to the end of the 9-months follow-up period will be flagged; and
 - Patients with ≥ 1 HbA1c measurement after the 30-day post-index and within 2 months prior to the end of the 9-months follow-up period will be flagged;
- Exclude patients who had ≥ 1 claim for U-500R Kwikpen administration in the 9-month baseline period;
- Exclude patients who had ≥ 1 claim with a ICD-9/10-CM code (Appendix 1) for secondary diabetes, gestational diabetes, diabetes complicating pregnancy, childbirth, or puerperium, or non-clinical diabetes at any time during the 9-month baseline period;
- Exclude patients who had claims indicating pump use (Appendix 2) in the identification period;
- Exclude patients who had claims indicating TDD exceeding 2000 units/day at any time in the pre-index or post-index periods.

Note:

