5.3.2 Subject Groups

After applying the inclusion and exclusion criteria, our analysis will focus on the following cohorts.

Index Event 1a

- U-500R Syringe Initiators Cohort: Patients who initiated U-500R syringe administration (index event 1a) on their index date.

Index Event 1b

- U-500R Kwikpen Initiators Cohort: Patients who initiated U-500R Kwikpen administration (index event 1b) on their index date.

Index Event 2

- U-500R Device Switchers Cohort: Patients who switched from U-500R syringe to Kwikpen will be included in this cohort.

Note: U-500R syringe/ Kwikpen initiators cohorts who were identified based on the index event 1a or 1b were U-500R naïve patients who did not have any evidence of U-500R use prior to the index date; whereas patients in U-500R device switchers cohort identified from index event 2 had been exposed to U-500R prior to the index date due to U-500R syringe use.

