5.4 Time Periods

The study period will range from 01APR2013-31MAR2018 for VHA and LCED; and 01JUL2013-30JUN2018 for Truven MarketScan claims. The identification period will be 01JAN2014-30JUN2017 for VHA and LCED; and 01APR2014-30SEP2017 for Truven MarketScan claims; the baseline and follow-up periods will be 9 months pre- and 9 months post-index date, respectively (Figures 1-3).

[2018-7241 Study Identifier] Observational Study Protocol**5.5 Variables/Measures**

Table 3 presents the study variables and operational definitions.

Table 3 Variables and Definitions

Variable	Source	Definition
Exposure		
Insulin use	Truven: Outpatient pharmacy claims table VHA: Pharmacy file	Index Event 1a : any insulin use other than U-500R in the pre-index and U-500R syringe use in the post-index period; Index Event 1b : any insulin use other than U-500R in the pre-index and U-500R Kwikpen use in the post-index period; and Index Event 2 : U-500R syringe use in the pre-index and U-500R Kwikpen use in the post-index period.
Baseline Characteristics*		
Age	Truven: Inpatient service table, outpatient service table, outpatient pharmacy claims table VHA: Enrollment file	Age will be retained in the dataset as a continuous variable for groups aged 18-25, 26-35, 36-45, 46-55, 56-64, and ≥ 65 years.
Sex	Truven: Inpatient service table, outpatient service table, outpatient pharmacy claims table VHA: Enrollment file	A flag will be created for male and female patients.
Race (only VHA)	VHA: Enrollment file	A flag will be created for White, Black, and other race patients.
U.S Region (only Truven)	Truven: Inpatient service table, outpatient service table, outpatient pharmacy claims table	A flag will be created for patients belonging to Northeast, Northcentral, South and West regions
Medicare eligibility (Only Truven)	From Truven	A flag will be created for patients who are enrolled in Truven Medicare
Body mass index (BMI)	VHA: Vital Status file	BMI on the index date will be calculated and reported as a continuous variable.
Quan-Charlson comorbidity index (CCI) Score ¹⁶	Truven: Inpatient service table, outpatient service table VHA: Inpatient and outpatient files	Quan-CCI score will be constructed using enhanced ICD-9/10-CM codes for 17 different comorbid conditions.

[2018-7241 Study Identifier] Observational Study Protocol

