Claim gaps	Truven: Outpatient pharmacy claims table VHA: Pharmacy file	The average gap between prescription fills of insulins will be calculated in the pre- and post-index periods among all the study cohorts.
Concomitant medications ^{18,19,20}	Truven: Outpatient pharmacy claims table VHA: Pharmacy file	A flag will be created for patients prescribed antihyperglycemic agents (AHA): thiazolidinediones, sulfonylureas, biguanides, meglitinides, alpha-glucosidase inhibitors, DPP-4 inhibitors, bile acid sequestrants, fixed-dose combinations, GLP-1 receptor agonists, and amylin agonists (Appendix 1).

[2018-7241 Study Identifier] Observational Study Protocol

HbA1c ²¹	VHA: Lab file	The HbA1c value in the baseline and follow-up period for each index event will be reported. Baseline HbA1c (pre-index HbA1c) will be the HbA1c measurement -90/+30 days of the index date. For patients with multiple HbA1c measurements within this period, the measurement taken closest to the index event date will be reported as the baseline HbA1c value. The follow-up HbA1c value will be the HbA1c measurement taken furthest in the time period after the 30 day-post index event date. However, based on the sample size, HbA1c within 2 months prior to the end of the study follow-up will be considered as the post-index HbA1c.
Hypoglycemic events	Truven: Inpatient service table, outpatient service table VHA: Inpatient and outpatient files, Lab file and Pharmacy file	Hypoglycemia events in the pre-index and post-index period will be evaluated using the ICD-9 codes from the Ginde algorithm (Appendix 1) ²² or the presence of a cutoff of blood glucose ≤ 70 mg/dL, or any evidence of intramuscular glucagon administration (Appendix 1). Hypoglycemia event occurred on or after the index date will be considered as the follow-up hypoglycemia event; and hypoglycemia event occurred on or prior to - 1 day of the index date will be considered as the baseline hypoglycemia event. Number of hypoglycaemia events per patient per year (PPPY) will be reported in both the pre-index and post-index periods.
Prescribed TDD	Linked Truven claims and EMR data:	The prescribed physician TDD will be calculated, and will be reported both as continuous and categorical variable.

[2018-7241 Study Identifier] Observational Study Protocol

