All-cause health care total and out-of-pocket costs	Truven: Inpatient service table, outpatient service table, outpatient pharmacy claims table	All-cause health care costs for total and out-of-pocket costs including inpatient costs, outpatient costs, pharmacy costs, total costs (inpatient + outpatient + pharmacy), out-of-pocket inpatient costs, out-of-pocket outpatient costs, out-of-pocket pharmacy costs and total out-of-pocket costs (inpatient + outpatient + pharmacy) will be computed among T2DM patients before and after U-500R syringe initiation and U-500R Kwikpen initiation. Costs will be adjusted to 2018 US dollars using the annual medical care and drug costs components of the Consumer Price Index (CPI) to reflect inflation.
---	---	--

Note: When comparing the TDD, ADD, adherence, fill rates and claim gaps in the pre vs post-index periods among the U-500R device switchers, only the claims corresponding to U-500R (syringe in the pre-index and Kwikpen in the post-index) will be considered. To be more specific we will be looking only at the treatment patterns of U-500R alone rather than the regimen.

However, for the U-500R initiators, the regimen use (use of different types of insulin) in the pre-index period will be compared to the regimen use (U-500R + other insulins) in the post-index period.

[2018-7241 Study Identifier] Observational Study Protocol**6. Sample Size and Statistical Methods****6.1 Determination of Sample Size**

The preliminary sample sizes for the VHA databases from 2013-2018 are shown below. This study will use the most recently available 5 years of data.

Table 4. Preliminary Sample Size

Database	Counts
VHA (01APRIL2013-31MARCH2018)	
T2DM (ICD-9: 250.x0, 250.x2) + Humulin R U-500 Kwikpen (NDC: 00002882427, 00002882459)	4,120
≥2 HbA1c measurements	4,066
T2DM + Humulin R U-500 Vial (NDC: 00002850101)	5,863
≥2 HbA1c measurements	5,718

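### One vial claim at any time in the 9-month baseline makes a device switcher, so the before/after device contrast for HbA1c and hypoglycemia can partly absorb the effect of starting or restarting U-500R

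*Protocol*

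**What the plan says.** Section 5.3.1 sets the index date for switchers by the pen alone: "the first prescription claim for U-500R Kwikpen administration will be designated as the Index Event 2". Prior syringe use enters through one criterion, "Include patients who had ≥ 1 prescription claim for U-500R vial use in the 9-month baseline period", together with the absence of a Kwikpen claim in the baseline. The note in section 5.3.2 adds only that these patients "had been exposed to U-500R prior to the index date due to U-500R syringe use".

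The outcome windows count back from the Kwikpen date:

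- HbA1c eligibility (section 5.3.1): "Include patients who had ≥ 1 HbA1c measurement within 90-day pre-index event or 30-day post-index event".
- HbA1c value (Table 3, section 5.5): "Baseline HbA1c (pre-index HbA1c) will be the HbA1c measurement -90/+30 days of the index date", taking the value closest to the index date.
- Hypoglycemia (Table 3): "hypoglycemia event occurred on or prior to - 1 day of the index date will be considered as the baseline hypoglycemia event".

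Table 3 describes the switchers' exposure as "U-500R syringe use in the pre-index and U-500R Kwikpen use in the post-index period". The note closing Table 3, which begins "When comparing the TDD, ADD, adherence, fill rates and claim gaps in the pre vs post-index periods among the U-500R device switchers", restricts those measures to U-500R claims. It does not mention HbA1c or hypoglycemia.

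**The concern.** Primary Objective 2 and Secondary Objective 2a ask how HbA1c and hypoglycemia differ before and after a change of device. That requires the 'before' state to be U-500R by syringe. The criteria admit two other kinds of patient:

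- **Recent starters.** The first vial was filled shortly before the first Kwikpen claim, so much of the 'before' period was spent on the previous insulin.
- **Restarters.** A vial was filled early in the baseline and ran out, other insulin followed, and then came the Kwikpen.

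For both groups the before/after change includes the effect of moving on to U-500R. Section 3 says that HbA1c improves on moving from U-100 to U-500R, so the HbA1c distortion has a predictable direction, in favor of the pen. The initiator cohorts are protected by a 9-month period free of U-500R; the switcher cohort has no matching protection.

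**Working it through.** The protocol gives no switcher count, no distribution of time on the vial and no expected effect. Table 4 holds only raw VHA counts of vial and Kwikpen users. There is thus no planned figure to reproduce, and the check has three parts.

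**1. Does another rule close the gap?** None does. Section 5.3.2 requires exposure, not duration. The U-500R-only note leaves out both outcomes. The HbA1c and hypoglycemia models in section 6.4.1 adjust for age, sex, race, BMI, CCI, TDD and time (plus HbA1c for hypoglycemia), with no term for time on the syringe. Table 3 defines discontinuation as a gap of more than 60 days after run-out, but this is not used to decide whether vial use was ongoing at the switch.

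**2. Window arithmetic.** Let t be the days from a patient's first vial claim to the first Kwikpen claim, with a 9-month window of about 274 days.

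- Share of the hypoglycemia window before U-500R = 1 - t/274.
- HbA1c look-back days before the first vial claim = max(0, 90 - t).

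| t (days) | Hypoglycemia window before U-500R | HbA1c look-back days before first vial |
|---|---|---|
| 21 | 253/274 = 92% | 69 of 90 |
| 30 | 89% | 60 of 90 |
| 60 | 78% | 30 of 90 |
| 90 | 67% | 0 |
| 180 | 34% | 0 |

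By date, a recent starter's baseline HbA1c is affected only if t is under 90 and the selected value precedes the first vial claim. Hypoglycemia is affected by any vial start within the 9 months. For a restarter, if vial supply ended more than 90 days before index, the whole HbA1c look-back falls after it.

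The cohorts can also overlap, because Index Event 1a does not exclude later Kwikpen use. Take a first vial claim at day -30 relative to the Kwikpen, one HbA1c at day -40 and a last one at day +230. The vial follow-up ends at day 274 - 30 = +244. If no other value lies closer to either index date, the same pair of values can serve as before and after in both cohorts, once as syringe initiation and once as device switch.

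**3. Illustrative size. Every input here is an assumption.**

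HbA1c, with a true device effect of zero: spurious change = s x E, where s is the share of switchers whose baseline value predates U-500R and E is the initiation effect.

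- s = 10%, E = 0.5: 0.10 x 0.5 = 0.05 points.
- s = 30%, E = 1.0: 0.30 x 1.0 = 0.30 points.

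With an SD of change of 1.5, the smallest change significant at two-sided 0.05 is 1.96 x 1.5/sqrt(n): 0.131 at n = 500 and 0.093 at n = 1,000. The chance that the paired test rejects although the device does nothing is:

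- bias 0.05: 12% at n = 500, 18% at n = 1,000;
- bias 0.10 (s = 20%, E = 0.5): 32% and 56%.

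Hypoglycemia: let a share s start the vial evenly across the baseline, so that on average half of their window is before U-500R, and let R be the rate ratio on starting U-500R. The spurious rate ratio is 1/(1 - s/2 + s/(2R)).

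- s = 10%, R = 1.2: 1/(1 - 0.05 + 0.0417) = 1.01.
- s = 50%, R = 2.0: 1/(1 - 0.25 + 0.125) = 1.14.

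**The case against.** Several counter-arguments have force.

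- **Table 3 does not contradict the criterion.** A reader might infer that it labels all pre-index time as syringe use. It does not say so. The parallel entries for the initiators name use occurring within the period, and read that way the entry agrees with the one-claim rule. The point is one of design, not internal inconsistency.
- **Closest-to-index selection helps.** Taking the HbA1c nearest the index date favors later values, so an early value is used only when nothing closer exists.
- **Recent starters may be few.** Section 3 dates the first approval of U-500R to 1994, and section 5.1 calls the Kwikpen recently available. Many switchers may be long-standing vial users, and the share could lie below 10%.
- **The illustration is generous.** It gives every affected patient the full initiation effect, and its SD and sample sizes have no source in the protocol. At n = 100 the threshold would be 1.96 x 1.5/10 = 0.29, near the top of the assumed bias range.
- **Mandatory exclusions would cost sample size**, which section 5.1 already treats as a concern. A sensitivity analysis could also sit in an SAP that is not at hand.

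These arguments limit the size of the problem and weigh against a fixed exclusion rule. They do not remove the problem, because the cohort definition and the outcome windows are both set in the protocol and leave the route open.

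**Conclusion.** The concern holds in a limited form: as written, the rules let pre-U-500R or lapsed time stand as the 'before' state, so the device contrast can partly absorb a start or restart effect. The exposure is wider for hypoglycemia (any vial start within 9 months) than for HbA1c in recent starters (first vial claim under 90 days before index and the selected value drawn before it). The HbA1c part concerns VHA, LCED and the pooled data, since the Truven claims database has no laboratory values.

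The amount is unknown. The 0.05-0.30 HbA1c points and the rate ratios of 1.01-1.14 depend wholly on the assumed shares, effects and start dates, and with few recent starters the bias is small. A reader might infer that the contrast simply is the initiation effect and will be reported as a benefit or harm of the pen. The documents do not support that: the objective is only to determine differences, and nothing shows how many switchers are affected.

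**What to change.** For the Index Event 2 cohort:

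1. Count pre-index hypoglycemia only from the first vial claim (or from the start of the baseline if the vial was already in use), as a rate over that person-time.
2. Flag patients whose baseline HbA1c was drawn before or soon after the first vial claim. The sponsor should choose and state the run-in length. One internal reference point is that the plan already treats values up to 30 days after an index event as baseline.
3. Flag patients whose vial supply ran out more than 60 days before the index date, which is the plan's own discontinuation gap.
4. Report the HbA1c and hypoglycemia contrasts separately for established, current vial users and for recent starters and restarters. Base any device-switch conclusion on the first group.

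All of this uses claim and laboratory dates already held, and no patient need be dropped from the cohort. The cost is a smaller group with lower precision for the device-switch conclusion, plus some programming. The loss cannot be quantified until the distribution of time on the vial has been tabulated.

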5.3. Study Population

5.3.1 Selection Criteria

Patient selection criteria for the U-500R Syringe Initiators [Index Event 1a]:

- Include patients who had ≥ 1 prescription claim for U-500R vial during the identification period (VHA and LCED: 01JAN2014-30JUN2017; Truven: 01APR2014-30SEP2017)—the first prescription claim for U-500R vial will be designated as index Event 1a (U-500R syringe initiation), and the date will be designated as the index date;
- Include patients who had ≥ 2 claims with an ICD-9/10-CM code (Appendix 1) for T2DM in any position (primary/secondary) at any time prior to the index date;
- Exclude patients who had both T1DM and T2DM, had no oral anti-diabetic drug (OADs; Appendix 1) other than metformin, and the ratio between the number of T1DM and T2DM claims > 0.5 at any time in the study period (VHA and LCED: 01APR2013-31MAR2018; Truven: 01JUL2013-30JUN2018);
- Include patients who were aged ≥ 18 years on the index date;
- Include patients who had continuous health plan enrollment with medical and pharmacy benefits for ≥ 9 months pre- and post-index event;
- Exclude patients with no evidence of insulin including U-500R (any type; Table 2) in the 9 months pre-index period (baseline);

[2018-7241 Study Identifier] Observational Study Protocol

- Exclude patients with ≥ 1 prescription claim for U-500R use in the 9 months pre-index period;
- Include patients who had ≥ 1 prescription claim for any insulin other than U-500R in the 9-month pre-index period;
- Include patients who had ≥ 1 HbA1c measurement within 90-day pre-index or 30-day post-index event;
- Include patients who had ≥ 1 HbA1c measurement after the 30-day post-index period at any time in the 9-months follow-up period;
 - Patients with ≥ 1 HbA1c measurement after the 30-day post-index and within 30 days prior to the end of the 9-months follow-up period will be flagged; and
 - Patients with ≥ 1 HbA1c measurement after the 30-day post-index and within 2 months prior to the end of the 9-months follow-up period will be flagged;
- Exclude patients who had ≥ 1 claim with a ICD-9/10-CM code (Appendix 1) for secondary diabetes, gestational diabetes, diabetes complicating pregnancy, childbirth, or puerperium, or non-clinical diabetes at any time during the 9-month baseline period;
- Exclude patients who had claims indicating pump use (Appendix 2) in the 9-month post-index (follow-up) period;

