Mixed linear model will be used to evaluate factors associated with HbA1c level in the pre- and post-index periods among U-500R syringe initiators, U-500R Kwikpen initiators, and U-500R device switchers. Mixed linear model is used for studies with a longitudinal feature in which a continuous outcome variable is measured for the same subject repeatedly over the time period. Based on the distribution of the data, observations measured for the same subject are likely to be correlated over the study period and these data are considered as "multilevel" data. In addition, mixed linear model has a mixed effect consisting both fixed and random effects. For this objective, mixed linear model helps to evaluate the effect of both time varying and time-independent variables on the HbA1c, while taking into account for correlation due to multiple assessments from the same individual. In the current model, HbA1c level which is measured at two time intervals (before and after the index event; U-500R initiation/device switch), will be considered the dependent variable. Observed TDD will be considered as the time varying covariate in the model (measured both before and after the index event), and the time independent covariates include the demographic and clinical characteristics.

The complete list of covariates will include:

- age
- sex
- race
- BMI
- baseline CCI score
- observed TDD from claims
- time (pre/post)

Note: Age, sex, race, BMI, and CCI score will be assessed during pre-index period. Observed TDD will be calculated during the entire pre-index and post-index periods, respectively. Pre-index

[2018-7241 Study Identifier] Observational Study Protocol

HbA1c will be defined as the HbA1c measurement -90/+30 days of the index date. For patients with multiple HbA1c measurements within this period, the measurement taken closest to the index event date will be reported as the pre-index HbA1c value. Post-index HbA1c will be defined as the HbA1c within 2 months of the end of the follow-up period.

Adherence will not be included as one of the covariates here due to the high collinearity between time and adherence. Hence, further mediation analysis will be performed to determine the mediator effect of adherence on HbA1c.

Mediation Analysis:

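### The device-switcher entry criterion sets no 9-month limit on the follow-up HbA1c, so switchers can be admitted without a follow-up value for Primary Objective 2

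*Protocol*

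**What the plan says.** Section 5.3.1 lists entry criteria separately for the three cohorts. Index Events 1a and 1b both require at least one "HbA1c measurement after the 30-day post-index period at any time in the 9-months follow-up period". The parallel line for Index Event 2 requires only an "HbA1c measurement after the 30-day post-index period" and stops there. Under each of the three criteria sit two sub-items for tests near the end of follow-up. The second covers patients with a test "within 2 months prior to the end of the 9-months follow-up period will be flagged". These sub-items mark patients and exclude nobody.

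Section 5.4 sets one length for all cohorts: "the baseline and follow-up periods will be 9 months pre- and 9 months post-index date, respectively". The HbA1c row of Table 3 (section 5.5) opens with "The HbA1c value in the baseline and follow-up period for each index event will be reported" and then gives the selection rule: "The follow-up HbA1c value will be the HbA1c measurement taken furthest in the time period after the 30 day-post index event date". It adds that, depending on sample size, "HbA1c within 2 months prior to the end of the study follow-up will be considered as the post-index HbA1c". In section 6.4.1, the HbA1c model (Primary Objective 2) and the hypoglycemia model (Secondary Objective 2a) both state: "Post-index HbA1c will be defined as the HbA1c within 2 months of the end of the follow-up period".

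The note after the criteria in section 5.3.1 drops the HbA1c requirement in the Truven claims database. The point therefore concerns VHA, LCED and the pooled data only.

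**The concern.** The HbA1c criterion exists so that every patient in the cohort has a value before and a value after the index event. For initiators it does so: at least one value between day 31 and month 9 is guaranteed. For switchers it does not, because a single test at month 14 would satisfy it. Follow-up ends at month 9, so that patient counts as a member of the switcher cohort but has no HbA1c in the follow-up period.

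Primary Objective 2 is affected directly. The paired t-test loses the patient. The mixed model receives a baseline value with no partner. In Secondary Objective 2a the post-index record would lack its HbA1c covariate. The reported cohort size and baseline table would describe more switchers than the before/after comparison uses.

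Entry criteria are usually programmed line by line, so a limit present in two cohorts and absent in the third is likely to be carried out literally.

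**Working it through.** **1. The plan's own calendar (VHA and LCED).** Inputs from section 5.4: identification 01JAN2014 to 30JUN2017, study period 01APR2013 to 31MAR2018, 9 months either side of the index date.
- 01JAN2014 minus 9 months = 01APR2013, which matches the study start.
- 30JUN2017 plus 9 months = 30MAR2018, one day short of the study end.

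The calendar is therefore built around a 9-month follow-up for the latest index date. Earlier index dates leave calendar time after month 9 in which a late test could satisfy the switcher criterion.

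**2. How far the open criterion reaches.** Reach = 31MAR2018 minus index date. Excess = 31MAR2018 minus (index date + 9 months).

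| Index date | Reach (days) | Excess past follow-up (days) |
|---|---|---|
| 01JAN2014 | 1,550 | 1,277 (about 42 months) |
| 01JAN2016 | 820 | 546 |
| 01JAN2017 | 454 | 181 |
| 30JUN2017 | 274 | 1 |

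With the initiators' wording, reach is 9 months (about 274 days) and excess is 0 for every index date.

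**3. Share of admitted switchers with no HbA1c in follow-up.** The protocol gives no test frequency, switcher count or switch dates, so these are assumptions:
- HbA1c tests follow a Poisson process at r = 2, 3 or 4 a year.
- Data run to 31MAR2018 for everyone.
- Switches accrue evenly to 30JUN2017 from one of three start dates.

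Let W = 244/365.25 = 0.668 years (days 31 to 274) and let X be the years from day 274 to 31MAR2018.
- No test inside follow-up: a = exp(-rW). This is 0.263, 0.135 and 0.069 for r = 2, 3 and 4.
- Admitted only through a late test: a × [1 - exp(-rX)].
- Admitted at all: 1 - a × exp(-rX).
- Affected share = mean of the second over index dates, divided by the mean of the third.

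Example, accrual from 01JAN2014 with r = 2: the mean of 1 - exp(-rX) is 0.857. The numerator is 0.263 × 0.857 = 0.225, the denominator is 0.962, and the share is 0.234.

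| Switches accrue from | r = 2 | r = 3 | r = 4 |
|---|---|---|---|
| 01JAN2014 | 23% | 12% | 6% |
| 01JAN2016 | 20% | 11% | 6% |
| 01JUL2016 | 17% | 10% | 5% |

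The range is about 5% to 23%. It falls if tests are evenly spaced or if enrolment ends soon after the required 9 months. With the limit added, the share is 0 by construction.

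**The case against.** The best defence is that this is a drafting slip with the answer given elsewhere. Both sub-items under the switcher criterion refer to the 9-month follow-up, section 5.4 gives one follow-up length for all cohorts, and section 6.4.1 ties the modelled value to the end of follow-up. That is probably right about intent. It does not repair the entry rule: the same sub-items stand under the initiator criteria, where the limit is still written into the main line, and they exclude nobody.

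A reader might go further and infer that switchers would be scored on HbA1c values taken years after the switch, unlike initiators. The documents do not support this. The inference needs the Table 3 sentence on the furthest measurement to be read alone, against the opening of the same row, the 9-month follow-up and both model definitions. That sentence also applies to all three cohorts. The initiator criterion guarantees a test within 9 months but does not cap which test counts as the furthest, so an open reading would reach initiators too. What remains is that the sentence has no end date of its own for any cohort.

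Three further points limit the weight:
- Lacking the modelled value is not peculiar to switchers. Under the last-2-months definition (about days 213 to 274), an initiator whose only later test falls on days 31 to 212 also lacks it. What differs is that initiators are guaranteed some value in follow-up.
- The 5% to 23% is assumed, not documented. Its upper end uses switches from January 2014, although section 5.1 describes the Kwikpen as a recent arrival on the market, and only 9 months of enrolment after the index date is required.
- Cohorts are analysed separately, before against after. No test of switchers against initiators on HbA1c change is specified, so the difference in criteria does not bias a planned between-cohort contrast.

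**Conclusion.** The point holds as a defect in one entry criterion. As written, the switcher cohort for VHA, LCED and the pooled data can include patients with no HbA1c between day 31 and month 9, which the criteria for both initiator cohorts rule out. These patients cannot contribute a before/after change, so the stated cohort can be larger than the analysed one.

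That the text allows this is certain. How many patients are affected is not: about 5% to 23% of admitted switchers under the testing, accrual and data-coverage assumptions shown, fewer under regular testing or earlier loss of enrolment, and none for switches at the very end of identification. The missing end date in the Table 3 sentence is a lesser, separate ambiguity common to all cohorts, since the surrounding text implies the 9-month bound. The correction is worth making because it changes who enters the cohort.

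**What to change.** - In section 5.3.1, complete the Index Event 2 criterion with the limit already used for Index Events 1a and 1b, so that it requires at least one "HbA1c measurement after the 30-day post-index period at any time in the 9-months follow-up period".
- In the HbA1c row of Table 3, state that for all three cohorts the follow-up HbA1c must lie after day 30 and on or before the last day of the 9-month follow-up.

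The cost is one phrase in the criteria and one in Table 3. The switcher count may fall slightly, but only by patients with no HbA1c inside follow-up, who could not have contributed to the paired comparison. The Truven claims analyses are unchanged.
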